7. STUDY OUTCOMES

The primary outcomes of interest are:

- Re-operation (revision, incision, excision, removal) or mesh removal
- Chronic pain, defined as pain persisting at least three months after surgery⁴⁹
- Voiding symptoms, defined as recurrence of incontinence or new retention.

All outcomes are determined in the surveillance period after surgery. Re-operation or mesh removal is defined as a surgery for any kind of mid-urethral sling, urethral bulking agent, bladder neck pubovaginal sling (autologous or allograft), or revision for mesh exposure. Resumption of voiding symptoms was defined as subsequent urinary retention, urinary incontinence, and sling revision for urinary retention. Chronic pain is defined as a new post-operative pain score >3 of 10 on vital sign data occurring over at least 3 months or greater of duration, or diagnosis codes related to abdominal and pelvic pain.

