9. STATISTICAL ANALYSIS PLAN (SAP)

9.1 STATISTICAL METHODS

Each of the outcomes, exposures, and covariates will be analyzed for counts at each site and a summarization and report will be provided to characterize the data. Stratified reporting of those receiving surgery for SUI with mesh and those without mesh will be performed. While this will allow for indirect comparison of these sub-populations side by side, no direct statistical comparisons between the groups will be made.

Next, if the characterization of the data is sufficient for the task, we will pursue a Cox proportional hazards model analysis, with each of the outcomes assessed from the time of the surgery as a time-to-event. We will censor the time-to-event analysis with death or loss to follow-up, defined as a time period >2 years from last applicable encounter of primary care, Obstetrics & Gynecology, or Urology. The models will be executed at each institutional separately using LASSO Cox to determine the consistently included covariates in each institution²⁵. We will then use the final variable list and utilize the method described by Lu and colleagues that uses a distributed analysis approach to obtain an exact model solution without sharing case level data (only intermediate and aggregate model coefficients and matrices)⁴⁶.

Because bootstrapping combined with the distributed analysis method would be computationally intensive, we will utilize 10-fold cross validation across all sites for internal validation of the risk model. We will assess overall discrimination using Harrell's concordance statistic (C-statistic)⁴⁷. To provide calibration assessments, we will also evaluate the model at fixed time points of 1 year and 2 year for each outcome using the AUC and the Estimated Calibration Index (ECI)⁴⁸. The ECI looks at the squared difference between the predicted probability and an estimated observed probability, ranging between 0 and 100, with 0 meaning perfect calibration. Additionally, we will graphically analyze calibration by investigating the smoothed observed-to-predicted probability plot⁴⁸.

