		 Mesh exposure and erosion (ICD9/10 629.31, 629.32/T83.711, T83.721) Urinary Retention (CPT Code 53500, ICD 9/10 788.20, 788.21/R33.0, R33.8-R33.9) Urgency of urination (ICD9/10 788.63/R39.15) Urge incontinence (ICD9/10 788.31/N39.41) Bowel injury (ICD9/10 569.83/S36) Bladder/urethral injury (ICD9/10 596.6,867.0/S37) Infection (ICD9/10 686.9,998.5,999.3,998.51,998.59/T81) Retropubic hematoma (ICD 9/10 568.81,,568.81,459.0/K66.1) Retopubic hematoma (ICD 9/10 568.81,,568.81,459.0/K66.1) Retopubic hematoma (ICD 9/10 568.81,568.81,459.0/K66.1) Bulking Injection CPT 51715, ICD 9/10 59.72/ PCS 3E0K3GC Laparoscopic Retropubic Urethropexy CPT 51990, 51992, 51999 Abdominal Retropubic Urethropexy CPT 51840,51841 Needle Bladder Neck Suspension CPT 51845 Kelly plication CPT 57220 Cystourethroplasty CPT 51800 Subtypes: Stress incontinence, female/mixed incontinence (ICD9/10 625.6,788.33/N39.46) Stress incontinence (female) (male)(ICD10 CM N39.3) 		
Outcome	Mesh Removal	 General, CPT 57287-Removal or revision of sling for stress incontinence (fascia or synthetic) ***some erosions managed surgically may have been coded by a different CPT (i.e. 57295 revise vaginal graft via vaginal approach) and not CPT 57287, which indicates a sling revision/removal. 	Yes	Possible Options: (a surgery for any kind of mid-urethral sling, urethral bulking agent, black neck pubovaginal sling (autologous or allograft), or revision for mesh exposure). Represented as a Date, allows time-to-event analysis.
Outcome	Post-Procedural Pain	?, mix of vital sign (pain score >3 of 10 on vital sign data) and likely free text. Also, diagnosis codes related to abd/pelvic pain (if prior pain free).	Some portion	Would have to exclude prior chronic pain or detect specific mention of new pain (free text). Could analyze group with no pre-surgical pain,

Protocol 1				[15 July 2020]
				otherwise probably beyond scope. Date/Time of first post- op occurrence.

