Covariate	Chronic Pain	Admin codes, also possibly pain medication. Chronic suprapubic pain Chronic pelvic, groin, or leg pain- ICD 9/10 625.9, 338.29, 789.09/R10.2, G89.29, R10.30 Chronic postprocedural pain- ICD 9/10 338.28/G89.28 Dyspareunia- ICD 9/10 625.0/N94.10, N94.12, N94.11, N94.19	Med & admin both structured	Yale Team: After reviewing the variable list, it seems as if the proposed variables are ascertainable. However, there will be some variables that will be more difficult to capture, for instance, the "post- procedural pain" variable will likely require going through free text and notes to determine if a pain score has been recorded.'
Covariate & Outcome	Voiding symptoms: urgency, obstructive symptoms, urinary retention, UTI	Admin codes Urinary Retention ICD9/10 for 596.0, 598.1, 598.2, 598.8, 598.9, 599.6, 599.69, 788.2, 788.21, 788.29, 788.61, 788.62, and 788.65. ²⁸ Urinary Tract Infection (UTI)- >100,000 CFU of bacteria on urine culture and symptoms of UTI Recurrent UTI (\geq 2 in 6 months or \geq 3 in 12 month) Urgency Urinary Incontinence ICD 9/10 (788.31/N39.41) Urinary Retention Requiring Prolonged Catheterization ICD 9/10 788.20/R33.9 and CPT 51701 or 51702 Overactive bladder (OAB)- ICD10 N32.81 or SNOMED 762262008 Urinary Tract Infection ICD 9 599.0 Infection of Kidney, NOS ICD 9 590.9 Urinary Tract Infection, site not specified ICD 10 N39.0 Urinary incontinence ICD 9: 625.6 Stress urinary incontinence, female 599.82 Intrinsic sphincter deficiency 788.30 Urinary incontinence, unspecified 788.31 Urge incontinence 788.33 Mixed incontinence (male) (female) 788.34 Incontinence without sensory awareness 788.35 Post-void dribbling		recurrence of incontinence or new retention. subsequent urinary retention, urinary incontinence, and sling revision for urinary retention Capture as date/time SME determined that this may be hard to separate from pre- existing condition

Protocol 1				[15 July 2020]
		788.36 Nocturnal enuresis		
		788.37 Continuous leakage		
		788.38 Overflow incontinence		
		788.39 Other urinary incontinence		
		ICD10:		
		N39.3 Stress incontinence (female) (male)		
		N36.42 Intrinsic sphincter deficiency (ISD)		
		R32 Unspecified urinary incontinence		
		N39.41 Urge incontinence		
		N39.46 Mixed incontinence		
		N39.42 Incontinence without sensory awareness		
		N39.43 Post-void dribbling		
		N39.44 Nocturnal enuresis		
		N39.45 Continuous leakage		
		N39.490 Overflow incontinence		

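### Early pain codes and carried-over stress-incontinence codes can count as events in two of the three primary outcomes, and retention is under-captured in the ICD-10 years

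*Protocol*

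**What the plan says.** Section 7 introduces its list with "The primary outcomes of interest are" and names three: re-operation or mesh removal, chronic pain, and voiding symptoms. This point concerns the last two.

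**Chronic pain.** The list gives "Chronic pain, defined as pain persisting at least three months after surgery". The paragraph below it makes this operational as a new pain score above 3 of 10 "occurring over at least 3 months or greater of duration, or diagnosis codes related to abdominal and pelvic pain". In the Section 13 data-collection table, the Post-Procedural Pain row allows diagnosis codes on the condition that the woman had no pain beforehand. It records the event as "Date/Time of first post- op occurrence".

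**Voiding symptoms.** The Section 7 list speaks of incontinence that recurs or retention that is new. The paragraph below restates this as any subsequent retention or incontinence, or a sling revision for retention. The Section 13 row is headed "Voiding symptoms: urgency, obstructive symptoms, urinary retention, UTI" and classed as both covariate and outcome. Its incontinence codes include "625.6 Stress urinary incontinence, female" and the ICD-10 counterpart N39.3. Its main retention entry reads "Urinary Retention ICD9/10 for 596.0, 598.1, 598.2, 598.8, 598.9, 599.6, 599.69, 788.2, 788.21, 788.29, 788.61, 788.62, and 788.65".

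**Time origin.** Section 9.1 fits Cox models "with each of the outcomes assessed from the time of the surgery as a time-to-event" and evaluates them at 1 and 2 years. No blanking period, washout or code-free interval is stated anywhere.

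**The concern.** The study is meant to describe mid-term (beyond 1 year) and long-term (beyond 2 years) harm, and the FDA intends to use the results in regulatory decisions. If recovery pain and routine follow-up billing qualify as events, part of what is reported as chronic pain or recurrent incontinence is neither.

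In a time-to-first-event analysis there is a second effect. An early false event ends the woman's follow-up for that outcome, so a genuine later event cannot be counted at its own date. The prediction models would then partly learn who is seen and coded soon after surgery.

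**Working it through.** The protocol gives no expected rate or event count for these coded outcomes, so there is no figure to reproduce. The check sets the definitions side by side.

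**1. Pain.** The headline definition in Section 7 requires three months' persistence. In the operative definition the three months attach to the pain score only; the codes follow after an *or*. The appendix takes the first post-operative occurrence. Take a woman with no earlier pain and one pelvic-pain code two weeks after surgery. She fails the headline definition, meets the operative one, and is dated at two weeks. The appendix condition on prior pain removes women whose pain pre-dated surgery. It does not remove recovery pain.

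**2. Incontinence.** Section 5 admits only women operated on for stress incontinence, so 625.6 or N39.3 describes the reason for surgery in every one of them. Both codes are in the voiding list. The word for recurrence in Section 7 has no rule behind it; the operative text needs only a later code. A cured woman whose check-up is billed under the original diagnosis therefore qualifies. The appendix itself notes that this outcome may be hard to tell apart from the pre-existing condition, and gives no rule to do so.

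**3. Retention.** All 13 codes in the main retention list are numeric ICD-9 codes, despite the ICD9/10 label. The only ICD-10 retention code in that row is R33.9, under prolonged catheterization, and it counts only together with CPT 51701 or 51702. R33.0 and R33.8 to R33.9 stand in the Re-Operation row, as a subtype of mesh revision. Section 4 says that the data span both coding eras. This error lowers counts, the opposite direction to steps 1 and 2.

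**4. How steps 1 and 2 scale (illustration only).** Let *p* be the true event rate and *f* the share of women without the event who still receive a qualifying code.

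observed = p + (1 − p) × f; share of counted events that are real = p / observed

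For voiding, *p* is taken from the literature range in Section 1.1 (3–30% after retropubic and 0–16% after transobturator slings). That range is for voiding dysfunction, not for the Section 7 outcome. For pain, *p* = 5% is assumed. The documents give no value for *f*; 5% and 20% are assumptions.

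| Outcome | p | f | Observed | Observed / true | Share real |
|---|---|---|---|---|---|
| Voiding | 3% | 5% | 0.03 + 0.97 × 0.05 = 7.85% | 2.6 | 0.38 |
| Voiding | 3% | 20% | 0.03 + 0.97 × 0.20 = 22.4% | 7.5 | 0.13 |
| Voiding | 16% | 5% | 0.16 + 0.84 × 0.05 = 20.2% | 1.3 | 0.79 |
| Voiding | 16% | 20% | 0.16 + 0.84 × 0.20 = 32.8% | 2.1 | 0.49 |
| Voiding | 30% | 5% | 0.30 + 0.70 × 0.05 = 33.5% | 1.1 | 0.90 |
| Voiding | 30% | 20% | 0.30 + 0.70 × 0.20 = 44.0% | 1.5 | 0.68 |
| Pain | 5% | 5% | 0.05 + 0.95 × 0.05 = 9.75% | 2.0 | 0.51 |
| Pain | 5% | 20% | 0.05 + 0.95 × 0.20 = 24.0% | 4.8 | 0.21 |

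Any *f* above zero biases the rate upward. The size runs from negligible to severe, depending on two quantities the documents do not supply.

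**The case against.** The project is a proof of concept for EHR data, and the Cox models go ahead only if the data prove adequate. Each site reviews 50 to 100 charts, outcomes included, and the Mayo extraction is checked against a curated registry. These steps may well reveal the misclassification, and that stands. They do not set a rule that removes it, and the written definitions would still be the ones applied.

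Several stronger readings are tempting, but the documents do not support them:

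- *Codes on the day of surgery count.* Surgery is the time origin, but Section 7 speaks of surveillance after surgery without defining its start, and Section 1.1 speaks of outcomes past 1 year. The start of risk is undefined and inconsistent, not fixed at day 0.
- *Pain need not be new.* The appendix, tentatively, requires no prior pain, and the objectives refer to new or worsening pain. What is missing is the duration.
- *The appendix widens the voiding outcome to UTI, overactive bladder and prolapse.* The row serves both covariates and outcomes, and its notes repeat the Section 7 definition, so these codes may be baseline covariates. The protocol fails to say which codes play which role.
- *The models would read the retention gap as a calendar effect.* The time scale is time since surgery, and calendar year is not among the listed covariates. The gap means under-ascertainment and nothing more.

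**Conclusion.** The point holds as a defect in what the protocol states, not as something left for a later analysis plan. Followed literally, the pain-code route contradicts the protocol's own three-month definition, and the incontinence list counts the index indication as a possible recurrence. Both biases are upward, and their size cannot be determined from the documents. The percentages in the table rest on assumed miscoding rates and should not be quoted as estimates of inflation. The ICD-10 retention gap is a separate error that lowers counts. It affects a different component of the voiding outcome and should not be netted against the other two. The definitions should be corrected before outcomes are extracted, because two of three primary outcomes depend on them.

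**What to change.** 1. **Pain.** Count pain codes only from 3 months after surgery, with persistence shown by a repeat code or a qualifying pain score, since a single late code does not show persistence. State the minimum spacing of repeat codes, and date the event when the criterion is met. Make new-onset pain in women without prior pain codes the main analysis. Report worsening pain separately, because the objectives include it and a blanket exclusion would lose it.
2. **Incontinence recurrence.** Start the at-risk period 3 months after surgery. Require either a fixed code-free interval (for example 3 months, varied in sensitivity analyses) or re-treatment before a 625.6 or N39.3 code counts.
3. **Retention.** Define new retention as no retention code in the 12 months before surgery. Add R33.0, R33.8 and R33.9, which the appendix already uses elsewhere, to the retention list.
4. **Roles of codes.** Label the UTI, urgency, overactive-bladder and prolapse codes in the voiding row as covariates only, so that the outcome matches Section 7.
5. **Start of risk.** Reconcile the past-1-year wording in Section 1.1 with the time origin in Section 9.1.

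The cost is a set of code-list and date-window edits on retrospective data. There will be fewer and later events, and women coded for incontinence at every visit without re-treatment will not count as recurrences. Early post-operative events should therefore be reported separately.

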8. DATA QUALITY

We will access the routinely collected observational data from electronic health records at Vanderbilt University Medical Center, Lahey Hospital & Medical Center, Mayo Clinic, Weill-Cornell, and Yale New

Version 2.0 [15 July 2020]

Haven Health System for this study. In addition, we will have access to a manually collected and curated 3,472 patient case series at Mayo Clinic from 2002 to 2012 of patients that underwent surgery for incontinence, which will be used exclusively to validate the data quality of the electronic health record data extraction and transformation process for the overlapping time period (2002-2012). For the routine EHR data sources, the valid dates will be from 2010 to the most recently available data.

8.1 DATA COLLECTION AND MANAGEMENT

As shown in Figure 1, we will access the data in each institution through the PCORNet or OMOP common data models, which are a normalized sub-set of EHR data that allows standardization of data representation and analytic processes. All sites but Lahey have PCORNet instituted through participation in PCORNet, and Lahey has OMOP. There is a publicly available transform from OMOP to PCORNet that will be utilized to harmonize Lahey to PCORNet. The data available across all sites is limited to patient demographics, inpatient and outpatient administrative condition and procedure codes (ICD-9/10, ICD-9/10 Procedure, CPT, HCPCS, SNOMED-CT), medication orders and/or fills/administrations, laboratory test results, vital signs, and date of death. We prefer prescribing if both are available. The PCORNet common data models in each site except Lahey have undergone extensive data quality assessment through data characterization queries where gaps and systematic miscoding have been reported and addressed over the course of the PCORNet CDRN network lifespan.

[figure not shown]

Figure 1: Summary of data collection and data flow process at each site for the variable transformation and distributed regression portions of the project.

Each of the participating sites will supplement their existing CDM-based structured data with free text peri-operative documents for those patient cases that has mesh implantation for stress urinary incontinence, as defined and identified elsewhere. As procedural codes are date specific, all documents +/- 2 days of the administrative code date will be extracted. Notes will then be further filtered to include only 2 notes for each surgical case, the pre-operative planning note (Surgeon, Anesthesia, or Nursing) and the operative note. Sample size estimates are based on a number of referent publications.^{50,51} Each site will randomize their patient population and initially select 600 patient documents among 300 patients (2 documents per patient, the primary operative note and a random note from the other notes included) for each surgery. Each site will determine what the surgical approach is at the document level (document assignment) and patient level (merging the 2 document assignments). Vanderbilt will annotate an additional 100 patients to serve as the primary training data set (100 training, 100 internal validation).

Version 2.0 [15 July 2020]

There are no patient recruitment or retention barriers in this project as all data are observational cohort data. There are significant issues around data ascertainment bias that will be addressed in more detail in Study Design & Methods. Patient level data will not leave each institution, only aggregate data or distributed regression analyses, which will remove the requirement for a data sharing agreement and streamline the execution of the project.

8.2 MONITORING PLANS

This is an observational study design, and there are no direct interventions for patients, thus a Data and Safety Monitoring Plan is not required, and a Data and Safety Monitoring Board is not required.

9. STATISTICAL ANALYSIS PLAN (SAP)

9.1 STATISTICAL METHODS

Each of the outcomes, exposures, and covariates will be analyzed for counts at each site and a summarization and report will be provided to characterize the data. Stratified reporting of those receiving surgery for SUI with mesh and those without mesh will be performed. While this will allow for indirect comparison of these sub-populations side by side, no direct statistical comparisons between the groups will be made.

Next, if the characterization of the data is sufficient for the task, we will pursue a Cox proportional hazards model analysis, with each of the outcomes assessed from the time of the surgery as a time-to-event. We will censor the time-to-event analysis with death or loss to follow-up, defined as a time period >2 years from last applicable encounter of primary care, Obstetrics & Gynecology, or Urology. The models will be executed at each institutional separately using LASSO Cox to determine the consistently included covariates in each institution²⁵. We will then use the final variable list and utilize the method described by Lu and colleagues that uses a distributed analysis approach to obtain an exact model solution without sharing case level data (only intermediate and aggregate model coefficients and matrices)⁴⁶.

Because bootstrapping combined with the distributed analysis method would be computationally intensive, we will utilize 10-fold cross validation across all sites for internal validation of the risk model. We will assess overall discrimination using Harrell's concordance statistic (C-statistic)⁴⁷. To provide calibration assessments, we will also evaluate the model at fixed time points of 1 year and 2 year for each outcome using the AUC and the Estimated Calibration Index (ECI)⁴⁸. The ECI looks at the squared difference between the predicted probability and an estimated observed probability, ranging between 0 and 100, with 0 meaning perfect calibration. Additionally, we will graphically analyze calibration by investigating the smoothed observed-to-predicted probability plot⁴⁸.

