Next, if the characterization of the data is sufficient for the task, we will pursue a Cox proportional hazards model analysis, with each of the outcomes assessed from the time of the surgery as a time-to-event. We will censor the time-to-event analysis with death or loss to follow-up, defined as a time period >2 years from last applicable encounter of primary care, Obstetrics & Gynecology, or Urology. The models will first be developed at each institutional separately using LASSO Cox to predict time to event for each of the outcomes of interest. We will use the variables retained in any of the individual site models, and develop a Cox model using the method described by Lu and colleagues (WebDISCO) that uses a distributed analysis approach to obtain an exact model solution without sharing case level data (only intermediate and aggregate model coefficients and matrices)¹. This method is being used to protect patient data by processing it at the local institutions and only sharing intermediate modeling statistics (aggregates) between sites.

Because bootstrapping combined with the distributed analysis method would be computationally intensive, we will utilize 10-fold cross validation across all sites for internal validation of the risk model. We assessed overall discrimination using Harrell's concordance statistic (C-statistic). To provide calibration assessments, we will also evaluate the model at fixed time points of 1 year and 2 year for each outcome using the AUC and the Estimated Calibration Index (ECI). The ECI looks at the squared difference between the predicted probability and an estimated observed probability, ranging between 0 and 100, with 0 meaning perfect calibration. Additionally, we will graphically analyze calibration by investigating the smoothed observed-to-predicted probability plot.

Target Population:All women aged 18 or greater undergoing transvaginal surgery for stress
urinary incontinence with or without mid-urethral mesh sling implantation
are eligible for inclusion in the EHR data. Determination of the appropriate
mesh exposure during surgery will be determined through administrative
CPT procedure codes, as defined in the appendix. No exclusions will be
applied based on race or ethnicity. As a separate sensitivity analysis to
reduce potential lack of outcome ascertainment, we will exclude all
patients that do not also have continuity of care within the data site,

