defined as requiring at least one outpatient medicine specialty or relevant
(Obstetrics & Gynecology, Urology) sub-specialty encounter in the 12
months prior to implantation. For this sensitivity analysis, we will also
exclude patients with prior pelvic organ prolapse or stress urinary
incontinence surgeries. As an additional comparator population, we will

Synthetic Mid-Urethral Slings for Stress Urinary Incontinence in Women	
Protocol 1	

	identify all those who underwent a procedure for SUI but did not receive mesh implantation.
Description of Sites/Facilities:	The Participating Sites for this Study include Vanderbilt University Medical Center, Lahey Hospital & Medical Center, Mayo Clinic, Weill-Cornell, and Yale New Haven Health System. In addition, as a data quality validation check, we will have access to a manually collected and curated 3,472 patient case series at Mayo Clinic from 2002 to 2012 of patients that underwent surgery for incontinence ² . For the routine EHR data sources, the valid dates will be from 2010 to the most recently available data.
	As a preliminary assessment of data volume, each site queried their data for CPT 57288 sling operation for stress incontinence. VUMC had a total of 6,106 from 2010-2018, and an average of ~500 cases a year for the last 4 years. Mayo Clinic had a total of 5,413 cases from 2010-2018, and an average of ~500 cases a year for the last 4 years. Weill-Cornell had 887 cases from 2010 to 2019, and an average of 150 procedures a year over the last 4 years. Yale New Haven Healthcare System has data from 2013-2018, and about 170 procedures in the most recent 6-month period. Lahey Clinic had 108 surgeries in 2018, and an average of 84 procedures a year over the last 4 years.
Description of Study Intervention:	This is an observational study design, and there are no direct interventions for patients, thus a Data and Safety Monitoring Plan is not required, and a Data and Safety Monitoring Board is not required.
Study Duration:	1 year, Start Date 02/17/2020, End Date 03/15/2021.
Duration of Data Captured:	2010-2019 in EHR Data

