- Chronic clinical conditions will be aggregated using the Healthcare Cost and Utilization Project's Clinical Classification Software, which reduces all ICD-9/10 codes to 285 clinically meaningful groups⁴². The CCS has been updated to include ICD-10, which is important, as this project will span ICD-9 and 10 eras.
- Medication exposures will be aggregated using the PCORNet⁴³ instantiation of the RxNorm controlled vocabulary⁴⁴ and leveraging this vocabulary to the Anatomical Therapeutic Chemical (ATC) Level 4 groupings, which are clinically relevant drug classes.

Some co-variates may not be ascertainable in some participating sites' PCORNet CDM instances, and this will be explored and reported. Each of the outcomes, exposures, and covariates will be analyzed for counts in each site and a summarization and report will be provided to characterize the data at each site. Stratified reporting of those receiving surgery for SUI with mesh and those without mesh will be performed.

Next, if the characterization of the data is sufficient for the task, we will pursue a Cox proportional hazards model analysis, with each of the outcomes assessed from the time of the surgery as a time-to-event. We will censor the time-to-event analysis with death or loss to follow-up, defined as a time period

Version 2.0

[15 July 2020]

>2 years from last applicable encounter of primary care, Obstetrics & Gynecology, or Urology. The models will be executed at each institutional separately using LASSO Cox to determine the consistently included covariates in each institution⁴⁵. We will then use the final variable list and utilize the method described by Lu and colleagues that uses a distributed analysis approach to obtain an exact model solution without sharing case level data (only intermediate and aggregate model coefficients and matrices)⁴⁶.

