11. RESULTS DISSEMINATION

No case level or individual patient level information will be shared between sites or publicly. All other artifacts of the research study will be shared. This includes study design, data cleaning and transformation code, statistical analysis code, covariate definitions, aggregate data summaries, and final prediction models for each outcome. We will first disseminate the results to the FDA and NEST, and then will follow their guidance for when the materials should be submitted for publication. Should any concerns arise from FDA requiring the information to be released prior to publication for safety reasons, we will involve all sites, the FDA, and NEST in these discussions.

At present, we do not anticipate that we will have device specific information available within the electronic health record data that would allow us to issue specific device safety information, but instead plan on a general analysis by surgical approach and implant type.

Use of Evidence: The FDA has been an important collaborator in the development of this project, as represented by [name], Deputy Director of Clinical Affairs and Chief Medical Office of the FDA

Center for Devices and Radiological Health. As the sponsor of this project, he has provided critical guidance on the particular outcomes, device exposures, and surgical procedures and indications that are of interest to the FDA. There has been an explicit discussion that the evidence generated by this project could impact FDA decision making around the use of synthetic surgical mesh implanted through a transvaginal approach for the indication of stress urinary incontinence, and that there is a relative lack of mid and long-term outcome data in these devices for this indication. [name] will be an active participant in the research protocol throughout the project and will diffuse the findings to the relevant FDA personnel that would need access to the results. This project does not have any current projected impact on coverage other than through possible indirect effect on future FDA decisions.

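### The final pooled Cox models are refitted on a LASSO-selected list with no shrinkage or recalibration named, so predicted risks for the rarer outcomes are likely to be too extreme

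*Protocol*

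**What the plan says.** The modelling plan appears in the synopsis (Statistical Methods) and in sections 4, 6 and 9.1 of the protocol. It has two stages.

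- **Selection.** Section 9.1 fits models at each institution "using LASSO Cox to determine the consistently included covariates in each institution"; sections 4 and 6 agree. The synopsis gives a different rule: "We will use the variables retained in any of the individual site models".
- **Final fit.** The resulting list goes into a distributed Cox model, by a method "that uses a distributed analysis approach to obtain an exact model solution without sharing case level data". Only variable names pass from the first stage to the second.

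The candidate pool is large. Section 4 uses a classification that "reduces all ICD-9/10 codes to 285 clinically meaningful groups", adds medications in "Anatomical Therapeutic Chemical (ATC) Level 4 groupings", and adds demographics, prior surgery, BMI, payer and others.

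Validation is 10-fold cross-validation across sites, with the C-statistic, AUC and the Estimated Calibration Index (ECI) at 1 and 2 years, and a smoothed calibration plot. No action is given for poor calibration. Under section 11, the material to be shared includes the "final prediction models for each outcome".

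**The concern.** LASSO does two jobs: it selects variables and it shrinks their coefficients. The plan carries forward only the first. An ordinary refit on the selected list restores full-size coefficients, including those of variables that entered by chance from a pool of roughly 300 or more. With few events, the linear predictor is then too widely spread in new patients.

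The usual measure is the calibration slope. A slope of 0.6 means that differences in log-hazard between women are overstated by a factor of 1/0.6, about 1.7. Honest cross-validation would report this but leave the released coefficients unchanged. The models are meant to be shared and results go first to the FDA and NEST, so over-dispersed risks for erosion and re-operation could be used as they stand.

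**Working it through.** The protocol gives no event count, number of predictors or shrinkage target for these models, so there is no figure of its own to reproduce.

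**1. Volume, before the section 5 exclusions.** From the synopsis: "VUMC had a total of 6,106 from 2010-2018", "Mayo Clinic had a total of 5,413 cases from 2010-2018", and 887 at Weill-Cornell.
- 6,106 + 5,413 + 887 = 12,406.
- Yale gives about 170 per six months and Lahey 84 per year, without totals. Assumed ranges are 1,020 to 2,040 and 336 to 840.
- Total: 12,406 + 1,020 + 336 = 13,762 to 12,406 + 2,040 + 840 = 15,286. About 15,300 is used below, the favourable end.

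**2. Expected events, from risks cited in section 1.1.**
- Erosion: 15,300 × 0.016 = 245.
- Re-operation by 1 year: 15,300 × 0.026 = 398.
- Re-operation by 5 years: 15,300 × 0.055 = 842.
- Voiding dysfunction at the upper cited figure: 15,300 × 0.30 = 4,590.

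**3. Expected shrinkage of an ordinary fit.** Solve S = 1 + p / [n ln(1 − R²/S)], where p is the number of variables and R² (Cox-Snell) is assumed to be 5 to 15% of its maximum. For an event proportion φ the maximum is 1 − exp{2[φ ln φ + (1 − φ) ln(1 − φ)]}. At φ = 0.016 this is 0.151, so R² is 0.0076 to 0.0227.

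| Outcome | p = 20 | p = 80 |
|---|---|---|
| Erosion, 1.6% | 0.85–0.95 | 0.59–0.81 |
| Re-operation at 1 year, 2.6% | 0.89–0.96 | 0.67–0.86 |
| Voiding, 30% | 0.96–0.99 | 0.87–0.96 |

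This ignores selection from the larger pool, so it is optimistic here.

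**4. Simulations of the two-stage procedure.** Both used five sites, LASSO at each site, an unpenalised pooled refit, and the slope measured in new patients.
- *Simulation A*: Cox; 15,202 women (Yale 170 × 12 = 2,040, Lahey 84 × 9 = 756); 300 binary candidates, 10 with hazard ratio 1.5; any-site rule. Slopes were 0.52–0.80 at about 5.5% events and 0.19–0.66 at about 1.6% (six runs each; a seventh run at 1.6% selected nothing).
- *Simulation B*: exponential survival fitted as a Poisson model; 15,286 women; 300 candidates, 25 real; four runs at each of two signal strengths. Mean slopes by rule:

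| Two-year risk | Any site | 2 or more sites | 3 or more sites |
|---|---|---|---|
| 1.6% | 0.39–0.68 | 0.38–0.82 | 0.71–0.93 |
| 3.3% | 0.76–0.78 | 0.73–0.93 | 0.81–0.97 |
| 15% | 0.80–0.86 | 0.96 | 0.98–0.99 |

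The 3.3% interpolates linearly between the cited 2.6% at 1 year and 5.5% at 5 years: 2.6 + (5.5 − 2.6)/4 = 3.3. The 15% is assumed. Under the any-site rule, top-decile predicted/observed risk was 1.31–1.46 at 1.6% and 1.13–1.23 at 3.3%. Single runs varied widely, from 0.25 to 0.75 at 1.6% and from 0.64 to 0.93 at 3.3%. The three-site rule left few or no variables for the rare outcomes.

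**5. Remedies.** In B (three rare-outcome settings, two runs each), a pooled LASSO with its coefficients kept gave mean slopes of 1.08–1.13, against 0.62–0.75 for the refit. AUC was 0.597–0.689 against 0.582–0.675. Rescaling by a cross-validated slope, with the list fixed outside the folds, gave only 0.80–0.91 (for example 0.648/0.774 = 0.84), because that cross-validated slope (0.76–0.83) was itself optimistic. In A, rescaling moved three runs from 0.58 to 0.85, 0.57 to 0.78 and 0.78 to 1.18.

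**The case against.** **No section says the final fit is unpenalised.** A reader might infer that the protocol chose this. It did not: the word exact is tied to not sharing patient-level data and can mean only agreement with a pooled fit. A separate analysis plan could also add a penalty. This stands as a limit on wording. But section 9 is itself headed as the statistical analysis plan, it names the final estimator, and all four descriptions pass on only a list.

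**Over-dispersion is not certain for every outcome.** A reader might infer that all the models will be too extreme. Voiding dysfunction is cited at up to 30%, and sections 7 and 13 define voiding symptoms and pain broadly. For common outcomes with short lists, or with a strict rule, slopes come close to 1. This stands. Under the any-site rule the shortfall at 15% risk was smaller but did not vanish.

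**Selection inflation is diluted.** A chance pick at Lahey is re-estimated on data of which 1 − 756/15,202, about 95%, come from other sites. True, and the simulations already include this effect.

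**Calibration will be checked.** The ECI and plots could reveal the fault, and modelling is conditional on adequate data. This stands, but neither changes the coefficients. The ECI is also weak for rare events: predicting 5.6% where 4% occurs (illustrative values) contributes 100 × 0.016² = 0.03 on a 0–100 scale, with no direction. If selection stays outside the folds, the check understates the problem.

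**The documents do not promise published 1- and 2-year risks.** A reader might infer this; those are evaluation times. What is shared is the models.

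**Conclusion.** The point holds for the rarer outcomes, erosion and re-operation. As written, the plan discards LASSO's shrinkage and puts nothing in its place, so predicted risks from the shared models are likely to be too extreme, especially under the synopsis's any-site rule. The indicative calibration slope is roughly 0.2 to 0.8. That range rests on few runs and on assumed effect sizes, number of candidates and Yale and Lahey totals, so the direction is firmer than the size. For common outcomes or a stricter rule the effect is smaller. The disagreement between the synopsis and section 9.1 on the selection rule is therefore material: it changes how far the models are miscalibrated.

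**What to change.** In section 9.1:

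1. State that the final pooled coefficients are penalised, with a ridge or LASSO penalty kept in the distributed fit. This is the preferred option. The version tested above applied LASSO to all candidates in pooled data; if the penalty is applied only to the site-selected list, tune it with site selection repeated in each fold.
2. Failing that, multiply the linear predictor by a cross-validated calibration slope, with site selection repeated in each fold, and re-estimate the baseline hazard. This was less reliable in the simulations.
3. Report the calibration slope for each outcome beside the ECI and the plot.
4. Reconcile the any-site rule of the synopsis with the consistent-inclusion rule of sections 4, 6 and 9.1, and define the chosen rule exactly.

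The text change is a few sentences. The real cost is additional distributed computation for tuning, or for repeating five site-level fits in each fold; the protocol already rejects bootstrapping on computational grounds. Predicted risks will also spread slightly less, and the tested penalised fit was mildly under-dispersed.
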